# 5.6.2 Blinding Procedures

This is a double-blind study: the Sponsor, subjects, investigator staff, persons performing the assessments and data reviewers and statisticians will remain blinded to the identity of the study treatments.

Protocol No.: GSN000300	Compound No.: GKT137831
Protocol Version No.: Final 4.0; Amendment 3	Sponsor: Genkyotex
Protocol Date: 24 July 2018	Author: Cmed Clinical Services

The identity of the study treatments will be concealed by the use of IMPs which are all identical in packaging, labeling, schedule of administration, appearance and odor.

Randomization data will be kept strictly confidential, and will be accessible only to authorized personnel (e.g., unblinded pharmacist or authorized designee), until unblinding of the trial as described in the statistical analysis plan (SAP).

Unblinding will only occur for the following reasons:

- Subject emergencies (see Section 5.6.3)
- Scheduled and unscheduled safety reviews by the SMB (see Section 9.7)
- At the time of the interim analysis (see Section 10.3)
- At the conclusion of the study.

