# 5.6.3 Emergency Breaking of Assigned Treatment Code

If an emergency unblinding becomes necessary, the Investigator should notify the Sponsor/Medical Monitor prior to unblinding, if possible, unless identification of the IMP is required for emergency therapeutic measures. The result of the code break should not be revealed to the Sponsor/Medical Monitor. Unblinding will be performed through the IWRS. The Investigator will access the IWRS to access the subject's treatment code. The Investigator may always, for urgent safety reasons, break the blind at any time during the conduct of the study. If the blind is broken, the date, time and reason must be recorded in the subject's eCRF and any associated AE report.

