### 10.3 Planned Interim Analyses

An interim analysis is planned once 80-90% of the planned number of subjects to be randomized in the study have completed their Week 6 visit. The primary efficacy endpoint for the interim analysis is the percent change from baseline to the Week 6 visit in serum GGT. Only data collected for these

Protocol No.: GSN000300	Compound No.: GKT137831
Protocol Version No.: Final 4.0; Amendment 3	Sponsor: Genkyotex
Protocol Date: 24 July 2018	Author: Cmed Clinical Services

randomized subjects, prior to and including the date of the Week 6 visit for the last subject to be randomized into the interim analysis cohort, will be included in the interim analysis. The purpose of the interim analysis is to support decision making with regards to the further development of GKT137831. It is not intended to amend the study protocol or stop the trial due to futility or overwhelming efficacy.

In addition to the analysis of the percent change from baseline to Week 6 in serum GGT, the interim analysis will include supportive analyses of the absolute change from baseline to Week 6 in serum GGT, as well as absolute and percent change from baseline to Week 6 in serum levels of ALP, hsCRP, fibrinogen, ALT, AST, conjugated and total bilirubin, as well as the absolute and percent change in the APRI and FIB-4 scores. The specific contents of the interim analysis will be documented in the SAP.

The interim analysis will be conducted by the unblinded SMB statistician, who has no involvement with study conduct. The interim analysis outputs will be communicated to the SMB and to a predefined disclosure committee, to aid decision-making with regards to the further development of GKT137831. However, to maintain the integrity of the trial data, no unblinding information for individual subjects will be shared outside of the SMB. Detailed communication flow will be outlined in the SMB charter and SAP.

In addition to the interim analysis described above a SMB will oversee the safety of the participating subjects as described in Section 9.7.

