5.3 RANDOMIZATION AND BLINDING

Approximately 100 subjects will be randomly allocated to placebo or one of the 2 active treatment arms, according to a 1:1:1 randomization ratio stratified at study entry by disease severity level defined as baseline serum GGT < $2.5 \times ULN$ or $\geq 2.5 \times ULN$).

Accordingly, approximately 33-34 subjects will be allocated to each of the 3 treatment arms.

A master reproducible randomization list will be produced by or under the responsibility of Cmed accounting for block size and stratification. The Interactive Web-Based Randomization System (IWRS) will assign a unique randomization number in ascending, sequential order (with associated treatment arm) to the subject, based on the pre-determined randomization schedule. The system will assign the pre-determined blocks of randomization numbers for each stratification level to ensure similarly balanced treatment groups. Assignment will be in sequential order within blocks and stratification level. The investigator will enter the randomization number in the electronic case report form (eCRF).

The Sponsor, subjects, investigator staff, persons performing the assessments, data reviewers and statisticians will remain blinded to the identity of the study treatments.

The identity of the study treatments will be concealed by the use of Investigational Medicinal Products (IMPs) which are all identical in packaging, labeling, schedule of administration, appearance and odor.

Randomization data will be kept strictly confidential and be accessible only to authorized personnel (e.g., unblinded pharmacist or authorized designee), until unblinding of the trial as described in this SAP.

Unblinding will only occur for the following reasons:

- Subject emergencies (see Protocol Section 5.6.3 for more details)
- Scheduled and unscheduled safety reviews by the Safety Monitoring Board (SMB) (see Protocol Section 9.7 for more details)
- At the time of the interim analysis (see Section 9)
- At the end of the study.

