The interim analysis will be conducted by the unblinded SMB statistician, who has no involvement with the study conduct. The interim analysis outputs will be communicated to the Sponsor's Chief Medical Officer.

The interim analysis described above does not include assessments of safety data. The safety data will be reviewed periodically and separately as described in the study SMB charter.

10 Changes to Planned Analyses

The final analysis will be performed according to a 2-stage process detailed in Section 6.1.

11 Document History

Date	Version	Modified by	Brief details of changes made to template
150CT2018	1.0	[name]	Initial final version
15MAR2019	2.0	[name]	Updated final version The main changes are the following: 1. Addition of Section 6.1 to clarify the timing of the final analysis. 2. Addition of Appendix 1 to provide the list of Top Line tables.

12 References

[1] New Drug Application (NDA) 207999 submitted by Intercept Pharmaceuticals, Inc. for obeticholic acid (OCA) proposed for the treatment of Primary Biliary Cirrhosis (PBC), Gastrointestinal Drug Advisory Committee (GIDAC) Meeting, April 7th, 2016.

[2] Hirschfield GM et al. Efficacy of Obeticholic Acid in Patients With Primary Biliary Cirrhosis and Inadequate Response to Ursodeoxycholic Acid. Gastroenterology 2015; 148: 751-761.

[3] CTCAE v4.03:

http://evs.nci.nih.gov/ftp1/CTCAE/CTCAE_4.03_2010-06-14_QuickReference_5x7.pdf

13 Appendix 1: List of Top Line tables

Table order	Table number	Table title
1	14.1-1	Subject Disposition (Randomized Population)
2	14.1-3	Summary of Demographic and Baseline Characteristics (ITT Population)
3	14.1-5.1	Disease Characteristics (ITT Population)
4	14.2-1.1.1	Summary of Absolute and Percent Change from Baseline to Week 24 Visit in Serum GGT (ITT Population)
5	14.2-1.1.2	Analysis of Percent Change from Baseline to Week 24 Visit in Serum GGT (ITT Population)
6	14.2-1.3.1.1	Summary of Percent Change from Baseline to Week 24 Visit in Serum GGT by Subgroup of Baseline GGT values (ITT Population)
7	14.2-1.3.1.2	Analysis of Percent Change from Baseline to Week 24 Visit in Serum GGT by Subgroup of Baseline GGT values (ITT Population)
8	14.2-2.1.1	Summary of Absolute and Percent Change from Baseline to each Post- Baseline Visit in Serum GGT (ITT Population)
9	14.2-2.1.2	Analysis of Percent Changes from Baseline in Serum GGT across all Post Baseline Visits [a] Model Estimates (ITT Population)

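### SAP Section 9 sends the interim outputs to the Sponsor's Chief Medical Officer, while Protocol Section 10.3 sends them to the SMB and a disclosure committee; the two rules need reconciling

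*SAP*

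**What the plan says.** Protocol Section 10.3 sets the recipients: "The interim analysis outputs will be communicated to the SMB and to a predefined disclosure committee". It adds that "no unblinding information for individual subjects will be shared outside of the SMB", and leaves the rest to other documents: "Detailed communication flow will be outlined in the SMB charter and SAP".

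SAP Section 9 has the unblinded SMB statistician run the analysis, and then says: "The interim analysis outputs will be communicated to the Sponsor's Chief Medical Officer". It mentions neither the SMB nor a disclosure committee as a recipient. SAP Section 10, which records changes to the planned analyses, lists only the two-stage final analysis. SAP Section 3 says the SAP was prepared with reference to Protocol Version 4.0, the version reviewed here.

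On blinding, Protocol Section 5.6.2 says that "the Sponsor, subjects, investigator staff, persons performing the assessments and data reviewers and statisticians will remain blinded", and SAP Section 5.3 repeats this almost word for word. Each then lists the interim analysis among the occasions for unblinding. The Protocol refers the reader to its Section 10.3, and the SAP to its own Section 9.

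Both documents give the interim the same limited purpose: to inform further development of the product, with no intention to amend the protocol or to stop for futility or efficacy.

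**The concern.** A team following SAP Section 9 literally would send the outputs to one Sponsor officer. A team following Protocol Section 10.3 would send them to two bodies, neither of which is said to include that officer. The supplied text does not reconcile the two instructions.

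What is at stake is operational bias in a trial that continues after the interim. The interim endpoint is the primary variable, percent change in GGT, measured at Week 6 instead of Week 24. It is analysed once 80-90% of the planned subjects have reached that visit. Protocol Section 2.1.3.1 argues that GGT responds to other treatments within weeks, so by-arm results at Week 6 could hint at the Week 24 outcome. Nothing supplied keeps a recipient of those results out of later decisions about the trial's data or its analysis plan.

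**Working it through.** No power, alpha or sample-size figure bears on the point. The check is a comparison of texts, with one timing sum and one cohort sum.

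**Recipients**

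| | Protocol Section 10.3 | SAP Section 9 |
|---|---|---|
| Named recipients | SMB; predefined disclosure committee | Sponsor's Chief Medical Officer |
| Limit on content | No individual-subject unblinding outside the SMB | None stated |
| Committee membership | Not stated | Committee not mentioned |

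The Protocol names two bodies and the SAP names one officer. They have no recipient in common by name. That counts labels only, because the officer could be a committee member.

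**Blinding rules, followed through their cross-references**

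- Protocol Section 5.6.2: Sponsor blinded; interim exception; Section 10.3; SMB statistician, SMB and disclosure committee. No Sponsor officer is reached.
- SAP Section 5.3: Sponsor blinded; interim exception; Section 9; SMB statistician and Chief Medical Officer. A Sponsor officer is reached.

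The SAP is therefore consistent within itself on this point. The difference lies between the SAP and the Protocol.

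**What the outputs would show**

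SAP Section 9 states that baseline GGT, ALP, ALT and hsCRP are summarised by allocated group. It does not say so for the efficacy outputs. A development decision would need a comparison of arms, so by-arm efficacy results are a reasonable inference, but they remain an inference.

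**How much of the trial, and when**

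- Planned size, from the sample-size sections of both documents: 102. Cohort: 0.80 × 102 = 81.6 and 0.90 × 102 = 91.8, so about 82 to 92 subjects. The SAP adds that this is a minimum.
- The data cut-off is the Week 6 visit of the last subject in the cohort. For that subject the primary assessment is 24 − 6 = 18 weeks away. For subjects enrolled earlier the gap is shorter.

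**What is still open at that time**

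- Week 24 data are still being collected.
- Deviations are classified at the end of the study, before unblinding (SAP Section 7), with a final review before database lock (SAP Section 8.2). This sets the per-protocol (PP) population, which is supportive only. Its outputs are produced only if it is at least 10% smaller than the ITT population.
- Whether to run PP sensitivity analyses of secondary endpoints is decided after that review (SAP Section 8.7.2). Additional biomarker analyses may be added through a SAP change log (SAP Section 8.7.3).

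The documents do not say what part, if any, the Chief Medical Officer plays in these steps.

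**The case against.** The strongest reply is that the documents can be read together. Protocol Section 10.3 foresees disclosure beyond the SMB, delegates the detailed flow to the SMB charter and the SAP, and bars only individual-level unblinding. SAP Section 9 does not say the officer is the only recipient, and the SMB's own statistician runs the analysis. If the officer sits on the disclosure committee, the SAP's list is incomplete, not contradictory. Protocol Section 1 (Roles and Responsibilities) and the SMB charter were not available and may say so. This stands, and it is why confidence is only moderate. It does not supply the missing statement: power to detail a flow does not clearly extend to replacing the named recipients, and SAP Section 9 neither mentions the committee nor repeats the group-level limit.

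Existing safeguards also count. The statistician has no part in study conduct, ITT membership follows mechanically from randomisation and dosing, laboratory data come from a central laboratory, deviations are to be classified before unblinding, and the interim is not meant to alter or stop the trial.

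A reader might be tempted by four stronger readings.

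- **Both blinding sections shut this officer out.** They do not: SAP Section 5.3 points to the section that names the officer.
- **Protocol Section 5.6.3 shows that the Sponsor may see nothing.** It says "The result of the code break should not be revealed to the Sponsor/Medical Monitor", but it concerns a code break for one subject. Group-level results need not reveal any individual's treatment.
- **The choice between ANCOVA and the van Elteren test could be steered by the interim.** That choice rests on residual plots from a model that includes treatment, so it naturally comes after the Stage 1 lock, when Week 24 data are in use. Earlier knowledge of Week 6 results adds little.
- **The Sponsor's request for the first database lock suggests influence from interim results.** That lock is tied to the last Week 24 visit, and nothing links the request to interim results.

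**Conclusion.** The two documents name different recipients for the interim outputs, the SAP does not declare the difference, and their blinding exceptions lead to different people. This should be fixed before the outputs are released.

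The practical exposure is limited. One Sponsor officer may know Week 6 GGT results for about 82 to 92 of 102 planned subjects while Week 24 data are being collected and before the classification that sets the supportive PP population. The size of any bias cannot be estimated from the documents. It would be wrong to infer that the blind has been broken or that the primary ITT analysis is compromised: no individual codes are said to leave the SMB, and the officer's role in later decisions is not stated.

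This rests on two assumptions: that the interim efficacy outputs are by arm, and that neither Protocol Section 1 nor the SMB charter already resolves the matter.

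**What to change.** Amend SAP Section 9 in three respects.

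1. Name the Protocol Section 10.3 recipients: the SMB and the disclosure committee, with members listed by role. If the Chief Medical Officer is a member, say so.
2. State that recipients outside the SMB receive group-level results only.
3. Add one sentence that recipients outside the SMB take no part in deviation classification or SAP changes until the Stage 1 database lock. If the SMB charter already provides for this, cite it instead.

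The cost is a wording change to the SAP. No Protocol amendment is needed once SAP Section 9 matches Protocol Section 10.3, and sample size and analyses are unaffected. The drawback is that the officer, if a recipient, stays out of those decisions for a limited time.
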